## SYNOPSIS

Title:	An Open-Label, Dose-exploration, Cohort Study Evaluating the Efficacy and Safety of Voclosporin in Achieving Complete or Partial Remission of Proteinuria in Subjects with Focal Segmental Glomerulosclerosis
Short Title:	AURONA
Study Product:	Voclosporin
Indication:	Focal Segmental Glomerulosclerosis
Phase:	2
Sponsor:	Aurinia Pharmaceuticals Inc.
Study Code:	AUR-VCS-2017-03
Objectives:	
Primary Objective:
 
 
• To assess the efficacy of voclosporin in achieving complete or partial remission of proteinuria after 24 weeks of therapy in subjects with focal segmental glomerulosclerosis (FSGS).
 
 
Secondary Objective:
 
 
• To assess the safety and tolerability of voclosporin over 24 weeks in subjects with FSGS.
 

Design:	Open-label, 24-week, multicenter, exploratory cohort study of voclosporin.
Treatment:	
Investigational Treatment:
 
Voclosporin softgel capsules containing 7.9 mg drug. Up to 10 subjects will be enrolled into Cohort 1 and take voclosporin 23.7 mg orally (PO), twice daily (BID). The dose level of voclosporin for Cohort 2 (at least 10 subjects) will be determined by analysis of efficacy and safety data at Week 12 from the first 5-6 subjects in Cohort 1.

Inclusion Criteria:	
 
1. Written informed consent before any study-specific procedures are performed.
 
2. Male or female subjects with a minimum age of 18 years (or legal age of consent if >18 years) to 75 years of age, inclusive, at the time of consent.
 
3. Primary FSGS diagnosed by renal biopsy within 6 months prior to the screening visit. Biopsy results over 6 months prior to screening may be permitted following review with the Medical Monitor to confirm eligibility.
 


Inclusion Criteria (cont'd):
	
 
4. At initial screening assessment and at last qualifying assessment during screening period prior to baseline, FSGS subjects must have a urine protein creatinine ratio (UPCR) of <math>\geq 2.0</math> mg/mg. Subjects can be treatment-naïve or receiving steroid treatment (oral or IV) for FSGS. Subjects taking steroids must show signs of improvement in proteinuria, defined as at least a 20% improvement in UPCR from initiation of steroids to the last stability assessment prior to baseline. Subjects who have discontinued steroid treatment due to poor tolerability may be considered for the study. Subjects should also have a serum albumin level of <math>\leq 3.2</math> g/dL at screening and at the last qualifying assessment prior to baseline; subjects with serum albumin <math>> 3.2</math> g/dL may be included following review to confirm primary FSGS and after discussion with the Medical Monitor.
 
5. All subjects should be treated with angiotensin converting enzyme inhibitors (ACEIs) and/or angiotensin receptor blockers (ARBs) unless they have documented intolerance or contraindication to these medications. Doses of these agents must be stable for at least 2 weeks prior to baseline, with blood pressure (BP) <math>\leq 150/90</math> mmHg at the baseline visit (Visit 2). 
 
a) Subjects with nephrotic edema may be treated with diuretics during the screening period. Volume status should be optimized based on the clinical judgment of the Investigator and the doses of diuretics must be stable for at least 2 weeks prior to baseline.
 
b) At the discretion of the Investigator, subjects with hyperlipidemia may be treated with lipid-lowering agents (e.g., statins) in accordance with standard clinical practice. Doses must be stable for at least 2 weeks prior to baseline.
 
 
 
6. Stable proteinuria, renal function, and BP for at least 2 weeks prior to baseline, as assessed by the Investigator. Changes in UPCR, estimated glomerular filtration rate (eGFR), and/or BP during the screening period may be due to treatments administered (e.g., ACEIs and ARBs); and, therefore, may interfere with study assessments or outcomes, or may place the subject at increased risk. All subjects must be discussed with the Medical Monitor prior to initiation of study treatment.
 
7. Women of childbearing potential must have a negative serum pregnancy test prior to dispensing study treatment. Two effective forms of contraception must be used simultaneously unless abstinence is the chosen method. Subjects must use effective contraception during the study.
 


Exclusion Criteria:
	
 
1. Subjects unable or unwilling to give written informed consent and/or to comply with study procedures.
 
2. Clinical or histologic evidence of secondary FSGS.
 
3. Histologic evidence of collapsing variant FSGS.
 
4. eGFR as calculated by the Chronic Kidney Disease Epidemiology Collaboration (CKD-EPI) equation of <math>\leq 30</math> mL/minute/1.73 m^2 at initial screening assessment or <math>\leq 45</math> mL/minute/1.73 m^2 at last qualifying assessment during screening period prior to baseline.
 


Exclusion Criteria (cont'd):
	
 
5. Currently taking or expected to require any of the prohibited medications listed in the protocol at screening or during the study. This includes prior use of cytotoxic or other immunosuppressant treatment for FSGS. Subjects who have discontinued steroid treatment due to lack of response are excluded from the study.
 
6. Currently requiring renal dialysis (hemodialysis or peritoneal dialysis) or expected to require dialysis during the study period.
 
7. A previous renal transplant or planned renal transplant during the study.
 
8. Body mass index >40 kg/m^2 at last stability assessment.
 
9. Family history of nephrotic syndrome.
 
10. Any known hypersensitivity or contraindication to cyclosporine, or components of any cyclosporine drug product.
 
11. Current or medical history of: 
 
• Congenital or acquired immunodeficiency.
 
• In the opinion of the Investigator, clinically significant drug or alcohol abuse within 2 years prior to screening.
 
• Malignancy within 5 years of screening, with the exception of basal and squamous cell carcinomas treated by complete excision. Subjects with cervical dysplasia that is cervical intraepithelial neoplasia 1, but have been treated with conization or loop electrosurgical excision procedure and have had a normal repeat Papanicolaou test are allowed.
 
• Current or past lymphoproliferative disease or previous total lymphoid irradiation.
 
• Severe viral infection (e.g., cytomegalovirus, hepatitis B virus, hepatitis C virus) within 3 months of screening, or known HIV infection. Severe viral infection is defined as active disease requiring antiviral therapy.
 
• Active tuberculosis (TB) or known history of TB/evidence of old TB if not taking prophylaxis with isoniazid.
 
 
 
12. Other clinically significant active medical conditions, such as: 
 
• Severe cardiovascular disease including congestive heart failure, history of cardiac dysrhythmia or congenital long QT syndrome. Subjects with QT interval duration corrected for heart rate using method of Fridericia exceeding 480 msec in the presence of a normal QRS interval (<110 msec) at time of screening are excluded.
 
• Liver dysfunction: aspartate aminotransferase, alanine aminotransferase, or bilirubin ≥2.5 times the upper limit of normal at last qualifying assessment during screening period prior to baseline.
 
• Chronic obstructive pulmonary disease or asthma requiring oral steroids.
 
 
 

---	---

Exclusion Criteria (cont'd):
	
 
• Bone marrow insufficiency: white blood cell count <math><2,500/\text{mm}^3</math>, absolute neutrophil count <math><1.3 \times 10^3/\mu\text{L}</math>, and/or thrombocytopenia (platelet count <math><50,000/\text{mm}^3</math>) at screening or at last qualifying assessment during screening period prior to baseline.
 
• Current infection requiring intravenous antibiotics.
 
 
13. Any overlapping autoimmune condition for which the condition or the treatment of the condition may affect the study assessments or outcomes (e.g., any condition for which additional immunosuppression, including systemic corticosteroids, and/or cytotoxic therapy is indicated). Overlapping conditions for which the condition or treatment is not expected to affect assessments or outcomes are not excluded.
 
14. No vaccines using live organisms, viral or bacterial, are allowed during screening and while taking the study treatment.
 
15. Other major physical or psychiatric illness or major traumatic injury within 6 months prior to screening that may affect study conduct or interfere with study assessments or outcome.
 
16. Any other medical condition which, in the Investigator's judgment, may be associated with increased risk to the subject or may interfere with study assessments or outcomes.
 
17. Subjects who are pregnant, breast feeding or, if of childbearing potential, not using adequate contraceptive precautions.
 
18. Participation in another interventional clinical study within 4 weeks prior to screening and/or receipt of investigational drugs within 4 weeks or 5 half-lives of the drug (whichever is longer) prior to screening.
 
19. Subjects treated in a previous voclosporin clinical study.

Primary Endpoint:
	
Proportion of subjects with remission of proteinuria at Week 24, assessed overall and for each individual cohort, based on the following parameters:
 
 
• Complete remission: UPCR of <math><0.3 \text{ mg/mg}</math>
 
 
OR
 
 
• Partial remission: UPCR <math>\geq 0.3 \text{ mg/mg}</math> and <math><3.0 \text{ mg/mg}</math> with <math>>50\%</math> reduction in UPCR from baseline
 


Secondary Endpoints:
	
The following secondary endpoints will be assessed overall and for each individual cohort:
 
 
• Proportion of subjects with complete remission or partial remission of proteinuria at Weeks 8 and 12
 
• Proportion of subjects with complete remission of proteinuria at Weeks 8, 12, and 24
 
• Proportion of subjects with UPCR <math><0.5 \text{ mg/mg}</math> at Weeks 8, 12, and 24
 
• Proportion of subjects with partial remission of proteinuria at Weeks 8, 12, and 24
 

[figure not shown]

Secondary Endpoints (cont'd):
	
 
• Time to first occurrence of complete or partial remission of proteinuria
 
• Time to first occurrence of complete remission of proteinuria
 
• Time to first occurrence of partial remission of proteinuria
 
• Time to first occurrence of 50% reduction in UPCR from baseline
 
• Duration of UPCR <0.3 mg/mg
 
• Change from baseline in UPCR at each time point
 
• Proportion of subjects with a confirmed >30% decrease from baseline in eGFR (utilizing the CKD-EPI formula) at each time point
 
• Proportion of subjects with a confirmed >30% increase in eGFR from the final visit (Week 24 or last on-treatment visit, for subjects who discontinue prematurely) to the second Safety Follow-up visit (Visit 10)
 
• Change in UPCR from the final visit (Week 24 or last on-treatment visit, for subjects who discontinue prematurely) to the second Safety Follow-up visit (Visit 10)
 
• Change in eGFR from the final visit (Week 24 or last on-treatment visit, for subjects who discontinue prematurely) to the second Safety Follow-up visit (Visit 10)
 
• Change from baseline in serum creatinine, serum albumin, and eGFR at each time point
 
• Quality of life assessments 
 
– Mean change in Patient Reported Outcome Measurement Information System (PROMIS) measures at Week 24
 
– Change from baseline in Kidney Disease Quality of Life-Short Form (KDQOL-SF™) score at Week 24
 
 
 
• Safety and tolerability over 24 weeks
 
• Renal biopsy: descriptive analyses of changes in histopathology will be evaluated in post-treatment (24 weeks) renal biopsies in a subset of patients
 
• Change from baseline to Weeks 4 and 24 in the following biomarkers: 
 
– Urine nephrin
 
– Urine synaptopodin
 
– Serum transforming growth factor beta
 
 
 

--------------------------------------	---

Procedures:	
See Schedule of Events for full details of protocol-required procedures and applicable visits (and timings).
 
Subjects who have provided signed and dated informed consent will be screened for entry into this study. Subjects will be assigned a unique subject number which will be used to identify them throughout the study. If a subject has not had a renal biopsy within the required timeframe for study eligibility, one may be performed to assess eligibility into the study, provided consent is in place and provided the results are received before the end of screening. The duration of the screening period will be approximately 4 weeks to 10 weeks (allowing for visit windows) to ensure that subjects meet eligibility criteria, including renal disease stability assessments.
 
The first 5-10 subjects meeting the required eligibility criteria will be assigned to Cohort 1 and will receive voclosporin according to the following dosing regimen:
 

• Week 1: 1 capsule (7.9 mg) PO, BID

• Week 2: 2 capsules (15.8 mg) PO, BID

• Week 3 – Week 24: 3 capsules (23.7 mg) PO, BID

 
Appropriate sponsor personnel (including the medical monitor) and the investigator will jointly decide whether to continue with the dose escalation for each subject.
 
When the first 5 or 6 subjects in Cohort 1 have completed 12 weeks of treatment with voclosporin, the top line efficacy and safety data will be analyzed to determine the dose level for Cohort 2. The selected dose may be higher or lower than 23.7 mg BID. The maximum dose possible for Cohort 2 will be 39.5 mg (5 capsules) BID. Should this dose be selected the following dosing regimen will be followed:
 

• Week 1: 1 capsule (7.9 mg) PO, BID

• Week 2: 2 capsules (15.8 mg) PO, BID

• Week 3: 3 capsules (23.7 mg) PO, BID

• Week 4 – Week 24: 5 capsules (39.5 mg) PO, BID

 
Evaluable safety and tolerability data at Week 12 from the first 5-6 subjects from Cohort 1 are required in order to make the decision to escalate to a higher dose level for Cohort 2.
 
As a guidance, the dose will not be escalated if any of following criteria are met in the first 5 or 6 subjects from Cohort 1, unless it was obvious that the occurrence was not related to the administration of voclosporin:
 

• Severe adverse events (SAEs) of same character in <math>\geq 2</math> subjects.

• Clinically significant decrease in eGFR in <math>\geq 5</math> subjects.

• Clinically significant laboratory abnormalities of same character in <math>\geq 5</math> subjects.

• Clinically significant abnormalities of electrolytes in <math>\geq 4</math> subjects.

• Clinically significant changes in vital signs of same character in <math>\geq 4</math> subjects.

-------------	---

Procedures (cont'd)	
Doses and dose increments smaller than anticipated may be proposed for Cohort 2 based on the safety and tolerability results from the Cohort 1.
 
All subjects will complete dosing through 24 weeks of study treatment and will have 2 Safety Follow-Up visits, 1 and 2 weeks after completion of treatment (i.e., at Week 25 and Week 26). Subjects who permanently discontinue study treatment before the Week 24 visit will return for all remaining study visits and assessments, including the 2 Safety Follow-Up visits, unless they have withdrawn consent.

Sample Size:	
As this is an exploratory study, sample size calculations are not required. It is estimated that approximately 20 subjects will be recruited, with up to 10 subjects in Cohort 1 and at least 10 subjects in Cohort 2.

Statistical Methods:	
Analysis:
 
All statistical analyses relating to the primary and secondary objectives will be undertaken at study closure and will incorporate all available data.
 
Given the small sample size, all analyses will be descriptive in nature. Confidence intervals (CIs) for proportions may be calculated but it is recognized that such intervals, being based on 20 patients, will be very wide. As an example, the 95% Clopper-Pearson CI for a proportion of 30% based on 20 patients is (11.9%, 54.3%).
 
Populations:
 
The efficacy analysis will be based on intent-to-treat (ITT) principles and will include all enrolled subjects (non-screening failures).
 
The per-protocol data set will include the subset of subjects in the ITT set who do not have any major protocol violations (to be defined).
 
The safety analysis set will consist of all subjects who receive at least 1 dose of study treatment.
 
Methods:
 
Top line efficacy (change from Baseline in UPCR) and safety data (AEs, eGFR, ECGs and vital signs) for the first 5 or 6 subjects in Cohort 1 completing 12 weeks of study treatment will be reviewed and based on those data the commencement of enrollment and the target dose for Cohort 2 will be determined.
 
The analysis of the primary endpoint, complete or partial remission of proteinuria at Week 24, will be conducted on the ITT set and confirmed with the per-protocol set (if applicable). Remission of proteinuria will be summarized and an exact 2-sided 95% CI for the remission rate will be calculated.
 
The analyses of the secondary endpoints will incorporate the use of 2-sided 95% CIs and are described below:
 
 
• Binary endpoints will be summarized using exact 2-sided 95% CIs.
 
• Endpoints measured as a time-to-event will be displayed using Kaplan-Meier methodology. Median time-to-event along with 2-sided 95% CIs will be displayed.
 

Statistical Methods (cont'd)	

• Other endpoints will be summarized by visit. Absolute values and differences between baseline and each time point up to and including Week 24 will be summarized using means and 2-sided 95% CIs. Changes between last on treatment value and post treatment follow-up will also be summarized.

 
Safety Endpoints:
 
Adverse events will be aggregated by System Organ Class and preferred term and presented as summary tables.
 
Laboratory values, vital signs, and other safety parameters will be summarized by visit as absolute values and change from baseline. Laboratory values outside of defined normal ranges will be summarized.
 
Exploratory analyses will be undertaken should the data suggest areas worthy of further investigation.

---------------------------------	---

# STUDY SCHEMA

Notes: BID=Twice daily; VCS=Voclosporin.

## AUR-VCS-2017-03 SCHEDULE OF EVENTS

Visit	Visit 1 Screening Period		Visit 2 Baseline	Visit 3	Visits 4-5	Visit 6	Visit 7	Visit 8 End of Treatment/ Early Termination	Visit 9 Safety Follow-up	Visit 10 Safety Follow-up
Day/Week	Screening to Day -1		Day 1 (Within 1 Wk Post Qualifying Assessment)	Wk 2 (±3 Days)	Wks 4, 8 (±3 Days)	Wk 12 (±3 Days)	Wk 18 (±5 Days)	Wk 24 (±7 Days)	Wk 25 (±3 Days) or Premature Disc. +7 Days	Wk 26 (±3 Days) or Premature Disc. +14 Days
	Screening Visit 	Stability Assessments 1 & 2, Optional 3 & 4 								
Informed consent	✓									
Eligibility criteria	✓	✓								
Renal biopsy 								✓ 		
Medical history and demography	✓									
Physical exam 	✓		✓					✓		
Vital signs 	✓	✓	✓	✓	✓	✓	✓	✓	✓	✓
ECG 	✓		✓					✓		
Laboratory assessments 	✓	✓	✓	✓	✓	✓	✓	✓	✓	✓
Pharmacokinetics 					✓			✓		
Urinalysis and urine microscopy	✓		✓	✓	✓	✓	✓	✓	✓	✓
FMV urine collection 	✓	✓	✓	✓	✓	✓	✓	✓	✓	✓
24-hour urine 			✓			✓		✓		
QoL 			✓					✓	✓	✓
Pregnancy test 	✓	✓	✓	✓	✓	✓	✓	✓		
Adverse events	✓ 	✓	✓	✓	✓	✓	✓	✓	✓	✓
Concomitant medications	✓	✓	✓	✓	✓	✓	✓	✓	✓	✓
Dispense study medication/ compliance 			✓	✓	✓	✓	✓	✓ 		
First dose of study medication			✓ 							

- 1 Stability assessments to occur at 14-day intervals ( $\pm$  3 days) with first assessment approximately 2 weeks after the screening visit. Stability assessments 1 and 2 are mandatory; assessments 3 and 4 are optional if additional time is required for the subject's clinical status to stabilize. Note that the laboratory assessments and FMV results of the last stability assessment will be used as the qualifying values for eligibility. Enrollment of eligible subjects must occur within 1 week of the final stability assessment.
- 2 If a subject has not had a recent renal biopsy, one may be performed to assess eligibility for the study provided informed consent has been given. The biopsy must have been performed 6 months prior to the screening visit. Biopsy results over 6 months prior to screening may be permitted following review with the Medical Monitor to confirm eligibility. Repeat renal biopsies may be done at Week 24 in a subset of subjects at selected sites.
- 3 Complete physical exam at screening; abbreviated exam at all other visits.
- 4 BP, pulse, temperature, weight, and height. Height included at initial screening assessment only. At stability assessments, BP only will be included.
- 5 In the event that a subject is noted to have a QTcF value exceeding 500 msec, or an increase of  $>60$  msec from baseline, the ECG should be repeated within 24 hours. Further details provided in the study protocol.
- 6 Laboratory assessments will be performed according to the schedule in the study protocol. Subjects must be fasting for at least 8-12 hours at Baseline and at end of study/early termination visit.
- 7 Pharmacokinetic assessments will be done at Weeks 4 and 24. PK samples will be drawn prior to study treatment dosing (trough sample), and at 1, 2 and 4 hours post-dose. In the event a subject experiences an SAE or requires a dose modification or is withdrawn from treatment, a voclosporin sample should be taken, with a trough sample preferred.
- 8 The UPCR will be calculated both from the FMV and from standard urinalysis results. If the FMV is for some reason not available, then standard urinalysis from a 24-hour urine collection may be substituted as an exception but only after agreement is reached with the Medical Monitor.
- 9 24-hour urine collection should begin 2 days prior to the scheduled study visit in order not to coincide with the FMV sampling due on the day of the study visit.
- 10 Patient Reported Outcome Measurement Information system (PROMIS) and Kidney Disease Quality of Life-Short Form (KDQOL-SFTM).
- 11 Serum pregnancy test to be evaluated at central laboratory at Screening and Week 24; urine pregnancy test will be performed locally at all other visits as applicable.
- 12 If screening visit occurs on the same day as informed consent, any findings are to be recorded as Medical History. Any change since the date of signed consent and/or during the screening period would be considered an AE.
- 13 Subjects in Cohort 1, will be contacted by telephone at the end of Week 1 as a reminder to increase their dose to 2 capsules (15.8 mg) BID for 1 week, starting at Week 2. Subjects will be contacted again by telephone at the end of Week 2 as a reminder to increase their dose to 3 capsules (23.7 mg) BID, starting at Week 3, for the remainder of the treatment period. Subjects in Cohort 2, will also be contacted at the end of each week (as required) up to Week 4, as a reminder to increase their dose to the maximum selected for Cohort 2.
- 14 Compliance only.
- 15 First dose of study medication should occur in the morning the day after dispensing.

Notes: Subjects who discontinue therapy will be requested to attend their regularly scheduled study visits to the end of the study.

AE = Adverse event; BID = Twice daily; BP = Blood pressure; Disc. = Discontinuation; ECG = Electrocardiogram; FMV = First morning void; Min = Minimum; QoL = Quality of life; QTcF = QT interval duration corrected for heart rate using method of Fridericia; SAE = Serious adverse event; Wk= Week.

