## 9. STUDY PROCEDURES

### 9.1 Description of Study Assessments

#### 9.1.1 Laboratory Assessments

Analysis of all samples for hematology, chemistry, hepatic function, lipid profiles, and urinalysis will be performed at a central laboratory using standard validated methods (see the laboratory manual). All study data analyses involving laboratory values will be based on results from the central laboratory.

The UPCr will be calculated both from the first morning void (FMV) and from standard urinalysis results. If the FMV is for some reason not available at Day 1, Week 12 or Week 24, standard urinalysis from a 24-hour urine collection may be substituted as an exception but only after agreement is reached with the Medical Monitor.

Blood and urine samples for the following efficacy and safety assessments ([Table 1](#)) will be drawn in accordance with the [Schedule of Events](#).

**Table 1** Review of Laboratory Assessments

Test Type	Test Parameters	Collection at Visits
Hematology	Complete blood count (CBC) Hematocrit Hemoglobin Mean corpuscular hemoglobin (MCH) Mean corpuscular hemoglobin concentration (MCHC) Mean corpuscular volume (MCV) Platelet count Red blood cells (RBC) Red blood cell morphology White blood cells (WBC)	All
	Differential (absolute and %) Bands Basophils Eosinophils Lymphocytes Monocytes Neutrophils	All

Test Type	Test Parameters	Collection at Visits
Coagulation	Coagulation Activated partial thromboplastin time (aPTT) Prothrombin time (PT) Partial thromboplastin time (PTT)	Screening
Blood Chemistry	Alanine aminotransferase (ALT) Albumin Alkaline phosphatase (ALP) Aspartate aminotransferase (AST) Bicarbonate Bilirubin (direct and total) Blood urea nitrogen (BUN) Calcium Chloride	All
	Cholesterol (total, HDL, and LDL) & triglycerides Creatine kinase	Day 1 and Week 24
	Creatinine Gamma-glutamyl transferase (GGT) Glucose	All
	Glycosylated hemoglobin (HbA1c)	Day 1 and Week 24
	Lactic dehydrogenase (LDH) Magnesium	All
	Phosphorous, inorganic	Day 1 and Week 24
	Potassium Protein, total Sodium	All
	Urinalysis and urine microscopy	Complete urinalysis (to include urine protein, creatinine, blood, urine microscopy).
FMV urine collection	FMV will be performed to analyze UPCR.	All
24-hour urine	UPCR	Day 1, Week 12 and Week 24 Note that 24-hour urine collection should be scheduled so as not to coincide with the FMV sampling due on the day of the study visit

Test Type	Test Parameters	Collection at Visits

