### **10.2.4 Clinical Laboratory Evaluations**

A change in the value of a safety laboratory investigation can represent an AE if the change is clinically relevant in the opinion of the Investigator or if, during treatment with the study treatment, a shift of a parameter is observed from a normal value to a pathological value, or a further worsening of an already pathological value.

If, at the end of the treatment phase, there are pathological laboratory values which were not present at baseline, further clinical or laboratory investigations will be performed until the values return to within reference range or until a plausible explanation (e.g., concomitant disease) is found for the pathological laboratory values.

If the Investigator considers such an AE as serious it must be reported as an SAE.

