### **13.10 Safety Evaluations**

Specific safety endpoints are as follows:

- Biochemical (including liver function tests) and hematological laboratory tests

- AE profile and routine biochemical and hematological safety parameters
- Vital signs (BP, HR, temperature) at specific time points and change from baseline
- Standard 12-lead ECGs change from baseline
- Discontinuations from treatment
- Concomitant medications

Laboratory values, vital signs, and other safety parameters providing numeric data will be summarized by visit, and as change from baseline.

Adverse events and diseases will be coded using the latest available version of the Medical Dictionary for Regulatory Activities, the version of which will be provided in the clinical study report.

Treatment-emergent adverse events will be summarized by treatment arm, System Organ Class, and Preferred Term. SAEs, SAEs that led to death, and SAEs/AEs that led to withdrawal will also be summarized and listed.

Only AEs which started on or after the date of first dose of study treatment and up until 14 days after last dose will be considered TEAEs, though all AEs after informed consent will be recorded. SAEs occurring at any time after informed consent and prior to first study medication will be listed.

All prior and concomitant medications will be summarized using preferred terms and ATC Level 2.

Details of these and other analyses will be provided in the SAP.

All study data analyses involving laboratory values will be based on results from the central laboratory.

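### Glucose at Weeks 2-18 and 25-26 is summarised as change from a fasted Day 1 value, but fasting is neither required nor recorded at those visits

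*Combined protocol and SAP*

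**What the plan says.** All references are to the combined protocol and SAP.

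- **Fasting rule.** Schedule of Events, footnote 6: "Subjects must be fasting for at least 8-12 hours at Baseline and at end of study/early termination visit". No other visit carries a fasting rule. The treatment-visit procedures (Section 9.2.2) and the follow-up procedures (Section 9.2.4) add none, and neither asks for fasting status to be recorded.
- **Glucose schedule.** Section 9.1.1, Table 1 lists "Creatinine Gamma-glutamyl transferase (GGT) Glucose" in a row group collected at all visits.
- **Lipid and HbA1c schedule.** The same table gives "Cholesterol (total, HDL, and LDL) & triglycerides Creatine kinase" at Day 1 and Week 24 only, which are the two fasted visits. HbA1c has the same two time points.
- **Analysis.** Section 13.10: "Laboratory values, vital signs, and other safety parameters providing numeric data will be summarized by visit, and as change from baseline". The Synopsis (Safety Endpoints) adds: "Laboratory values outside of defined normal ranges will be summarized". Neither treats glucose separately or distinguishes a fasting from a non-fasting reference range.
- **Laboratory changes as adverse events.** Under Section 10.2.4, a laboratory change on treatment can represent an adverse event if, among other conditions, "a shift of a parameter is observed from a normal value to a pathological value".

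**The concern.** The fasting rule fits the lipid schedule but not the glucose schedule. A change from baseline is meaningful only if both values were taken under comparable conditions, and for glucose the main condition is whether the subject has eaten. At most visits the plan controls that condition for the baseline value and not for the later one.

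The study is single-arm and open-label (Section 4.1), so no concurrent group would show the same food effect and allow it to be discounted. With about 20 subjects, and about 10 per cohort, a few fed samples can move a visit mean. The reader of the safety tables, which serve the secondary objective (Section 3.2), could see glucose rise at Week 2, stay up to Week 18 and fall at Week 24 with no drug effect. Subjects who enter on corticosteroids taper over the same weeks (Section 7.1.2.2). That may also move glucose, and an unrecorded food effect makes the trend harder still to read.

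Fasting status has to be captured when the sample is drawn. It cannot be reliably reconstructed at database lock.

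**Working it through.** The plan states no figure on this point, so there is none to reproduce.

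**Step 1: visit count.** Inputs are footnote 6, Table 1 and the visit schedule (Section 4.1 and the Schedule of Events). Baseline for glucose is taken as the Day 1 value. The documents define baseline explicitly only for eGFR, but they label Day 1 as Baseline.

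| Visit | Glucose drawn | Fast required | Change from fasted Day 1 is like for like |
|---|---|---|---|
| Weeks 2, 4, 8, 12, 18 | Yes | No | Not assured |
| Week 24 | Yes | Yes | Yes |
| Weeks 25, 26 | Yes | No | Not assured |

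- On treatment: 5 of 6 changes, 5/6 = 83%, have no assured fast at the later visit.
- All post-baseline: (5 + 2) of (6 + 2) = 7 of 8, or 88%.

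The Week 24 entry applies to values observed there. Section 13.4 also describes a last-observation-carried-forward dataset. If that were applied to laboratory values, an interim glucose of unknown status could be carried into Week 24.

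**Step 2: size of the bias.** Let f be the share of subjects who have eaten before the draw and d the mean rise due to food. With no drug effect, the expected mean change at that visit is

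bias = f × d.

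Neither f nor d is in the documents. Assumed values, for illustration only:

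| f | d = 10 mg/dL | d = 20 mg/dL | d = 40 mg/dL |
|---|---|---|---|
| 0% | 0 | 0 | 0 |
| 25% | 2.5 | 5 | 10 |
| 50% | 5 | 10 | 20 |
| 100% | 10 | 20 | 40 |

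The range runs from zero to +40 mg/dL and depends entirely on f and d. What the documents establish is that f is neither controlled nor recorded.

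**Step 3: reach into the Week 12 dose decision.** The Synopsis (Procedures) lists, as guidance against escalation, "Clinically significant laboratory abnormalities of same character in" at least 5 of the first 5 or 6 subjects. Suppose food alone produced a clinically significant glucose abnormality in each subject independently with probability q (assumed).

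- q = 0.2, 6 subjects: P(at least 5) = 6 × 0.2^5 × 0.8 + 0.2^6 = 0.001536 + 0.000064 = 0.0016.
- q = 0.2, 5 subjects: 0.2^5 = 0.00032.
- q = 0.1, 6 subjects: P(at least 5) = 0.000055.

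The top-line safety data listed for that review (Synopsis, Statistical Methods) are AEs, eGFR, ECGs and vital signs. Glucose is not named.

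**The case against.** **Other rules may bring subjects in fasted.** Dosing is on an empty stomach (Section 7.1.2.1), the first-morning urine is due on the visit day, and Week 4 has pre-dose pharmacokinetic and biomarker samples (Section 9.1.6). This makes it implausible that every interim sample is fed, particularly at Week 4. But none of these rules sets fasting hours or ties the chemistry draw to food, so fasting remains uncontrolled.

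**Details may lie elsewhere.** Sections 13.1 and 13.10 defer detail to an SAP, and Section 9.1.1 cites a laboratory manual. Neither a separate SAP nor the manual or eCRF is available here, and any of them could hold a fasting field or a reference-range rule. That is fair. Still, Section 13.10 as written covers all numeric laboratory values.

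**The design limits the harm.** Day 1 and Week 24 form a fasted pair with HbA1c at both, and a rise that vanishes at a fasted Week 24 with flat HbA1c would itself suggest an artefact. This stands, and it is the main reason the point is minor. It does not correct the interim rows.

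**Stronger readings that a reader might infer, and that the documents do not support:**

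- *That false shifts to high glucose would be common.* Assume a fasting mean of 5.2 mmol/L, between-subject SD 0.4 and within-subject SD 0.3 (total 0.5), upper limits of 5.6 or 6.1 mmol/L, and a mean food shift of 0.5 to 2.0 mmol/L (SD 0.5). Simulation then gives 26-91% of subjects normal at Day 1 and high at a later visit, against 2-10% for fasted pairs. Every input comes from outside the documents, and the 26-91% requires every later sample to be fed. At limit 6.1 and shift 1.0, a 25% fed share gives 0.25 × 52.5% + 0.75 × 2.4% = 15%, and no fed samples gives 2.4%. At limit 5.6, which is (5.6 − 5.2)/0.5 = 0.8 SD above the mean, about 21% would already be high at baseline.
- *That fed values will become adverse events.* Section 10.2.4 says only that a change can represent one. It names a pathological value, not a fasting limit, and the investigator then judges relatedness (Section 10.2.2).
- *That the Week 12 dose decision is compromised.* Step 3 shows that this route is remote.
- *That a known risk is being obscured.* Section 1.2.4 names raised blood pressure and renal dysfunction as the well-known class toxicities. It does not name hyperglycaemia.

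**Conclusion.** The mismatch is confirmed by the text and needs no outside assumption: 5 of 6 on-treatment and 7 of 8 post-baseline glucose changes compare a fasted value with one of uncontrolled and, on the documents available, unrecorded fasting status. The consequence is conditional. Food can appear as a drug-period rise or an out-of-range value, by an amount f × d that the documents do not allow anyone to estimate and that is zero if subjects attend fasted.

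Severity is minor. The point concerns one safety analyte in a descriptive study of about 20 subjects. The observed Week 24 change, the HbA1c change and the primary endpoint are unaffected, and the Week 12 dose decision is not materially affected. It is still worth correcting before data accrue, because the missing item cannot be recovered later.

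**What to change.** 1. Add fasting yes/no to the eCRF at every glucose draw, unless the eCRF or laboratory requisition already holds it.
2. In Section 13.10 and the SAP, restrict the glucose change-from-baseline summary, and any out-of-range summary that uses a fasting range, to samples recorded as fasted, at whichever visit they occur. Interim samples that were in fact fasted are valid pairs with Day 1 and should be kept.
3. Tabulate non-fasted values separately by visit as random glucose, without change from baseline. If carried-forward values are used for laboratory data, do not carry a non-fasted glucose into the fasted Week 24 summary.
4. Present the Day 1 to Week 24 fasted change beside HbA1c as the main glycaemic reading.

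The cost is one extra eCRF field and some SAP wording, with no new sample or visit. The downside is fewer subjects in the glucose change table at interim visits. The steroid taper remains a separate influence on glucose that this change does not remove.
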